## 2.4 Alendronate Background

Bisphosphonates are synthetic analogs of pyrophosphate that bind to the hydroxyapatite found in bone. ALN (Fosamax®), a bisphosphonate that acts as an inhibitor of osteoclast mediated bone resorption, is indicated for the prevention and treatment of osteoporosis in postmenopausal women. Two trials of three-year duration demonstrated

significant increases in BMD at the lumbar spine, femoral neck and hip trochanter in response to ALN therapy.

Results of those trials and those of the Fracture Intervention Trial three- and four-year studies demonstrated significant reductions in the incidence of one or more new vertebral fractures in women with or without prevalent vertebral fractures at baseline, and incidence of hip fractures, and in the incidence of nonvertebral fractures compared with placebo (Black et al, 1996; Cummings et al, 1998; Fosamax® product insert).

The Fracture Intervention Trial consisted of two placebo-controlled studies in postmenopausal women: a 3-year study of patients with at least one baseline radiographic vertebral fracture and a 4-year study of patients with low bone mass but without a baseline vertebral fracture (Black et al, 1996; Cummings et al, 1998). The 3-year study (in patients with at least one baseline radiographic vertebral fracture) demonstrated that treatment with ALN resulted in statistically significant reductions in fracture incidence compared with placebo. The incidence of at least one new vertebral fracture was decreased from 15.0% to 8.0% (47% RRR). In the 4-year study (in patients with low bone mass but without a baseline vertebral fracture) the incidence of at least one new vertebral fracture was reduced from 3.8% to 2.1% (44% RRR).

Additional information is provided in the ALN package insert.

## 2.5 Calcium and Vitamin D Background

Calcium and vitamin D are important in the formation of bone matrix and for its subsequent mineralization where calcium found as calcium hydroxyapatite ( $\text{Ca}_{10}[\text{PO}_4]_6[\text{OH}]_2$ ) provides bones and teeth tissue with its strength. Calcium and vitamin D are therefore considered key components of therapy in the management of postmenopausal osteoporosis (PMO) (Dawson-Hughes et al, 2010) and have been required as background therapies in all contemporary therapeutic trials in PMO. Because of the active bone formation and mineralization that is expected with romosozumab, calcium and vitamin D supplementation will be necessary in order to achieve and maintain positive bone balance. The recommended dietary allowance and tolerable upper intake level of dietary calcium recommended by the US Institutes of Medicine for women over the age of 50 years on a western diet is 1,200 mg and 2,000 mg per day respectively. The recommended dietary allowance and tolerable upper intake level of dietary vitamin D for women aged 51-70 years is 600 IU and 4,000 IU per day respectively while the recommended dietary allowance and tolerable upper intake level of dietary vitamin D for women over the age of 70 years is 800 IU and

4,000 IU per day respectively (IOM 2010; Ross et al, 2011). The initial loading dose of 50,000 to 60,000 IU of vitamin D for subjects with vitamin D levels of  $\geq 20$  ng/mL and  $\leq 40$  ng/mL (administered within 1 week of the study day 1 visit) is necessary to provide a sufficient calcium pool for the expected and significant increase in bone mass and needed for bone mineralization in the first several months after initiation of treatment with romosozumab. This dose has been shown to be safe and well tolerated (Giusti et al, 2010; Tucci, 2009). The daily supplementation required in this study, that at a minimum should be in the range of 500 to 1,000 mg elemental calcium and 600 to 800 IU of vitamin D, is safe and represents commonly used and accepted doses for clinical trials in osteoporosis and are consistent with existing treatment practice and guidelines (Dawson-Hughes et al, 2010, IOM 2010).

## 2.6 Rationale

This will be a multicenter, international, randomized, double-blind, alendronate-controlled study of romosozumab in postmenopausal women with osteoporosis who have had a previous osteoporotic fracture and now require therapy for secondary prevention.

### Choice of control group

Alendronate was chosen as a control because it permits assessment of effects of romosozumab on fracture risk reduction in postmenopausal women with osteoporosis compared with the effects of a commonly used therapy for osteoporosis. Alendronate has shown to be effective in reducing vertebral fractures and its safety profile is well characterized (Black et al, 1996; Cummings et al, 1998; Fosamax® product insert).

However, in postmenopausal women with osteoporosis, fracture risk remains elevated despite continued treatment with alendronate (Black et al, 2006; Schwartz et al, 2010). Therefore an alendronate-controlled trial will provide a relevant comparison with a commonly used therapy for postmenopausal women with osteoporosis.

### Endpoints

Primary, secondary, and safety endpoints have been selected to describe the efficacy in fracture risk reduction, and the safety profile of romosozumab. The primary endpoint of subject incidence of clinical fracture captures established markers of efficacy for the treatment of osteoporosis: nonvertebral fractures and clinical vertebral fractures. Nonvertebral fractures and clinical vertebral fractures account for the bulk of significant morbidity and mortality related to osteoporosis. A decrease in the subject incidence of clinical fracture will therefore represent an improvement in the clinical burden from

osteoporosis. The primary endpoint of subject incidence of new vertebral fracture represents an established endpoint for registration of new osteoporosis therapies.

The proposed safety endpoints will permit evaluation of the risk/benefit profile of romosozumab compared to alendronate in postmenopausal women with osteoporosis through the assessment of reported adverse and serious adverse events, vital signs, laboratory data and formation of anti-romosozumab antibodies.

### **Inclusion criteria**

This study will enroll postmenopausal women with osteoporosis who meet at least one of the following BMD and fracture criteria:

- BMD T-score  $\leq -2.50$  at the total hip or femoral neck and either at least one moderate (SQ2) or severe (SQ3) vertebral fracture or at least 2 mild (SQ1) vertebral fractures

or

- BMD T-score  $\leq -2.00$  at the total hip or femoral neck and either at least 2 moderate (SQ2) or severe (SQ3) vertebral fractures or a fracture of the proximal femur that occurred within 3 to 24 months prior to randomization

The risk of fracture in this study population is high, and the subjects are likely to derive significant benefit from a bone forming agent in clinical practice.

### **Exclusion criteria**

Since all patients in the study will receive active treatment (either romosozumab or ALN), there is no lower threshold of BMD T-score as an exclusion criterion, nor is there an exclusion criterion based on higher numbers or severity of prevalent fractures.

The exclusion criteria for disease state, medical and medication history were chosen to minimize the possibility of influencing or confounding the results of the comparative assessment of efficacy and safety of two treatments administered in the study. In addition, subjects who have a contraindication to alendronate or unable to take alendronate oral tablets in accordance with the package insert are to be excluded.

### **ALN study period**

Clinical experience with anabolic agents such as teriparatide and PTH (1-84) strongly support the strategy of consolidating gains from anabolic therapy in new bone matrix that is either mineralized or in the process of being mineralized with a subsequent period of anti-resorptive therapy (Black et al, 2005; Prince et al, 2005). The sequential therapy with ALN following romosozumab treatment for 12 months is justified by the

anti-resorptive mechanism of action of ALN and the established clinical paradigms currently in use with anabolic agents ([Black et al, 2005](#); [Rittmaster et al, 2000](#); [National Osteoporosis Foundation 2010](#)).

### **Final analysis**

The study will continue beyond the time of primary analysis to allow following of subjects for the secondary endpoint of nonvertebral fractures.

### **2.7 Clinical Hypotheses**

The primary clinical hypotheses are that romosozumab treatment for 12 months followed by ALN treatment compared with ALN treatment alone is effective in reducing the incidence of clinical fracture (nonvertebral fracture and clinical vertebral fracture) and new vertebral fracture in postmenopausal women with osteoporosis. It is expected that romosozumab treatment for 12 months followed by ALN treatment will reduce the incidence of clinical fractures by 30% and the incidence of new vertebral fractures by 50% compared with the control group (ALN alone).

The primary safety hypothesis is that romosozumab treatment for 12 months is well tolerated in postmenopausal women with osteoporosis.

## **3. EXPERIMENTAL PLAN**

### **3.1 Study Design**

This is a phase 3 multicenter, international, randomized, double-blind, ALN-controlled study of romosozumab in postmenopausal women with osteoporosis. The study is designed to evaluate if romosozumab treatment for 12 months followed by ALN treatment, compared with ALN treatment alone, is effective in reducing the incidence of clinical fracture (nonvertebral fracture and clinical vertebral fracture) and new vertebral fracture.

After signing the informed consent form (ICF), subjects will undergo a screening phase to complete eligibility assessments. Upon confirmation of eligibility, approximately 4,000 subjects will be randomized 1:1 (approximately 2,000 subjects per arm) to receive either 210 mg romosozumab subcutaneous (SC) QM or 70 mg ALN orally (PO) every week (QW) in a blinded fashion for the duration of the 12-month double-blind ALN-controlled study period. Randomization will be stratified by age (< 75 years, ≥ 75 years). Subjects will also receive matched placebo for either ALN or romosozumab. After the initial 12-month study period, subjects will receive ALN while

remaining blinded to their initial treatment assignment (romosozumab or ALN). The primary analysis period will end and the primary analysis will be performed when:

- clinical fracture events (nonvertebral fracture or clinical vertebral fracture) have been confirmed for at least 330 subjects
- AND
- all subjects have had the opportunity to complete the Month 24 study visit.

If more than 330 subjects have confirmed clinical fractures at the time each subject has completed her Month 24 visit, the primary analysis will be based on all available data, which may include more than 330 events.

Upon completion of the primary analysis period, subjects will continue to be followed for the secondary endpoint of nonvertebral fractures. Subjects and site personnel will remain blinded to initial treatment assignments. The study will proceed in an event-driven manner. The final analysis (end of study) will be performed when nonvertebral fracture events have been confirmed for at least 440 subjects across the lifetime of the study. The study may be terminated earlier if the primary analysis demonstrates superiority of romosozumab treatment for nonvertebral fracture risk reduction (see [Section 10.2](#) for details on testing strategy). Study completion constitutes either completion of primary analysis if superiority is proven for nonvertebral fractures or when at least 440 subjects have experienced a nonvertebral fracture.

From screening to end of study, subjects will receive daily calcium and vitamin D supplementation that at a minimum should be in the range of 500 to 1,000 mg elemental calcium and 600 to 800 IU vitamin D. In addition, subjects with a serum 25 (OH) vitamin D level of  $\geq 20$  ng/mL and  $\leq 40$  ng/mL at screening will receive an initial loading dose of 50,000 to 60,000 IU of vitamin D after randomization, preferably by the oral route. Subjects with a serum 25 (OH) vitamin D level of  $> 40$  ng/mL at screening may also receive the vitamin D loading dose at the principal investigator's discretion.

Approximately 200 subjects at participating centers will be enrolled in an Imaging and PK/BTM/Biomarker sub-study. Within this sub-study, a subset of approximately 100 subjects will participate in the imaging (DXA, QCT) portion of the sub-study.

If there is insufficient enrollment into the blood only portion of the sub-study, additional sub-study sites will be initiated. Subjects already on trial will be invited to participate and consent will be obtained for the use of blood samples from earlier time points for sub-study analyses.

From study start until primary analysis, an external, independent Data Monitoring Committee (DMC) will monitor unblinded safety data on an ongoing basis and consider efficacy data in order to assess the risk/benefit profile of romosozumab.

The overall study design is described by a [study schema](#) at the end of the protocol synopsis section.

The study endpoints are defined in [Section 10.1](#).

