### 7.3 Study Visits

#### 7.3.1 Study Day 1/Baseline

##### For all subjects

- PRO/ClinRO questionnaires: OPAQ SV, EQ-5D-5L, LAD, and BPI worst pain (should preferably be completed before any other study procedures are performed)
- Blood sample for serum chemistry, hematology, and anti-romosozumab antibody
- DXA scans of lumbar spine, submitted to the central imaging vendor as soon as possible following the visit

Note: DXA scans of the lumbar spine may also be obtained during the screening period prior to Day 1 to facilitate subject scheduling.

- Adverse event and concomitant medications data collection
- If applicable, vitamin D loading dose of 50,000 to 60,000 IU, preferably by the oral route. The initial vitamin D loading dose is to be administered within 1 week of the study day 1 visit. However, if the vitamin D loading dose is missed in this timeframe, it should be given as soon as possible thereafter.
- Oral IP (ALN/placebo) dispensation (blinded, 2-month supply)
- IP (romosozumab/placebo) injection (must be the last procedure)

Note: If the vitamin D loading dose is given by SC injection, vitamin D and IP should not be administered in the same anatomical location.

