##### For subjects participating in the Imaging and PK/BTM/Biomarker sub-study

- Blood sample for romosozumab levels
- Fasting blood sample for P1NP, sCTX, BSAP, and OC
- Blood sample for sclerostin and iPTH
- Blood sample (serum and plasma) for novel biomarker development
- For subjects also participating in the imaging components: QCT of the spine, submitted to the central imaging vendor as soon as possible following the visit

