#### **7.8 Laboratory Assessments**

##### **7.8.1 General**

All applicable screening and all on-study blood samples during the primary analysis period will be processed and sent to the central laboratory. Depending on the assessment, the central laboratory will be responsible for either performing the assays, or shipping samples to Amgen or a specialty laboratory for assay.

The central laboratory will be responsible for all screening and on-study serum chemistry, hematology, and serum 25 (OH) vitamin D tests. The central laboratory will provide a study manual that outlines handling, labeling, and shipping procedures for all serum samples.

Blood samples for BTMs, romosozumab levels, and anti-romosozumab antibodies will be processed by the central laboratory, sent to an appropriate secondary laboratory or sent to Amgen for analysis or further distribution to other laboratories.

Following the end of primary analysis period, all applicable on-study blood samples will be processed and analyzed at a local laboratory. Local laboratories will use the local laboratory's normal ranges. Local laboratory results will be monitored by the principal investigator and any adverse events supported by local laboratory results should be reported as an adverse event (please see [Section 9.1.2](#)).

All blood samples will be obtained by venipuncture before IP administration, when applicable, at the time points outlined in the Schedules of Assessments ([Appendix A](#)). The date and time of blood collection will be recorded in the subject's medical record. Samples for assessment of BTMs must be obtained from subjects in the fasted state as indicated in [Section 7.8.2](#).

[Table 1](#) outlines the specific analytes for the serum chemistry and hematology assessments, as well as other assessments to be conducted on blood samples.

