romosozumab or other protocol-specified therapy, as required, characterize antibody response, and characterize aspects of the molecule (eg, metabolites). Results from this analysis will be documented and maintained, but may not be reported as part of this study.

Additional subjects will be invited to participate in the blood only portion of the sub-study at the time of enrollment and in the case of insufficient enrollment, additional blood only sub-study sites will be initiated and subjects already on trial will be invited to participate with consent for blood collected earlier in the study to be used for sub-study analyses.

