### **7.8.2 Bone Turnover Markers**

Subjects participating in the Imaging and PK/BTM/Biomarker sub-study will have blood drawn at visits specified in [Section 7.3](#) and the Schedule of Assessments ([Appendix A](#)) for analysis of BTMs (P1NP, sCTX, BSAP, and OC).

Blood draws for BTMs must be obtained from subjects in fasting stage and before noon. Fasting stage is defined as overnight fasting. If overnight fasting is not feasible, at a minimum 8 hours fasting is required.

Results from BTM assessments are considered potentially unblinding and will not be reported to study-related personnel post Day 1/baseline.

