### **7.8.2 Sub-study BTM Efficacy Analysis Set**

The subset includes all randomized subjects who enrolled in the sub-study who have a baseline and  $\geq 1$  post-baseline reported BTM result at or before the time point under consideration and will be used to evaluate P1NP, BSAP, OC and sCTX. Subjects will be analyzed according to their randomized treatment assignment, regardless of treatment received.

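### If women join the blood sub-study late, stored samples drawn under no fasting rule can become their turnover-marker baselines, and the SAP does not screen for this

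*Protocol*

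**What the plan says.** **Late-joiner route.** Protocol 3.1 makes it conditional: "If there is insufficient enrollment into the blood only portion of the sub-study, additional sub-study sites will be initiated". Women already on trial are then invited, and "consent will be obtained for the use of blood samples from earlier time points for sub-study analyses". The text after Table 1 in Protocol 7.8.1 repeats this: "subjects already on trial will be invited to participate with consent for blood collected earlier in the study to be used for sub-study analyses". Neither place attaches a fasting condition or excludes turnover markers.

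**Fasting rule.** Protocol 7.8.1 states: "Samples for assessment of BTMs must be obtained from subjects in the fasted state as indicated in" Section 7.8.2. That section states: "Blood draws for BTMs must be obtained from subjects in fasting stage and before noon". Fasting means overnight or, failing that, at least 8 hours.

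**Visit lists.** At Day 1 (Protocol 7.3.1), the sub-study list asks for: "Fasting blood sample for P1NP, sCTX, BSAP, and OC". The list for all subjects asks for: "Blood sample for serum chemistry, hematology, and anti-romosozumab antibody". The second carries no fasting or time-of-day instruction. The lists for Months 1, 3, 6, 9 and 12 have the same split.

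**SAP.** Under SAP 6.2, signing the sub-study consent counts as enrolment. SAP 7.8.2 begins: "The subset includes all randomized subjects who enrolled in the sub-study who have a baseline and"; it goes on to require at least one later result. The window tables in SAP 13.1.1.5 and 13.1.1.6 take the last pre-dose evaluation as baseline. No fasting criterion, flag or sensitivity analysis appears there or in SAP 9.2.4 or 10.7.1.

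**The concern.** A woman who joins after Day 1 has no sub-study Day 1 draw. The only sample that can give her a marker baseline is one taken on the main schedule. Her visits after joining follow the sub-study schedule and are fasting. Her percent change then compares a standardised follow-up with a baseline of unknown fasting status and time of day.

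Every marker endpoint in the sub-study is a percent change from baseline, so one off-standard baseline affects all of that woman's visits after joining. The size and time course of P1NP, sCTX, BSAP and OC within each arm are results in their own right, and they are what could be misread.

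**Working it through.** The documents state no power or precision figure for the sub-study, so there is nothing to reproduce. The check sets the provisions side by side and then illustrates size.

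**1. Does the plan as written admit such baselines?**
- Stored samples may be used for sub-study analyses (Protocol 3.1 and 7.8.1).
- The draws concerned had no fasting or before-noon rule (Protocol 7.3.1, list for all subjects).
- The SAP accepts a late joiner once she consents and has a baseline and a later result (SAP 6.2 and 7.8.2).

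So it does, and nothing in the SAP stops it.

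**2. How many women?** The sub-study has about 200 women, of whom about 100 are in the imaging part (Protocol 3.1). The blood-only part is 200 − 100 = about 100. That is the ceiling, reached only if every blood-only participant joins late.

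**3. Effect on one woman.** Let f be the ratio of the stored baseline to the baseline she would have had under the fasting, before-noon rule. With a fasting follow-up and true change c, the reported change is (1 + c)/f − 1. The documents give no value for f, so 0.8 to 1.25 is an assumed range. The values of c are the phase 2 medians for 210 mg QM in Protocol 2.3.

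| f | sCTX, c = −26.3% | P1NP, c = −10.2% |
|---|---|---|
| 0.8 | −7.9% | +12.3% |
| 0.9 | −18.1% | −0.2% |
| 1.0 | −26.3% | −10.2% |
| 1.1 | −33.0% | −18.4% |
| 1.25 | −41.0% | −28.2% |

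For example, 0.737/0.8 − 1 = −7.9% and 0.737/1.25 − 1 = −41.0%.

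If follow-up and baseline share the same f, the reported change is f(1 + c)/f − 1 = c and nothing is distorted. A late joiner's visits before joining were also main-schedule draws, so the shift applies to visits after joining.

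**4. Effect on the arm summaries and the test.** The Wilcoxon rank-sum test of SAP 10.5.1.7 was simulated with 100 women per arm, log-scale SD 0.4, log-scale effect 0 or 0.18, late joiners spread evenly over arms, and 4,000 runs. All of these settings are assumptions. Results with half the women joining late, against none:

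| | none late | half late, f = 0.8 | half late, f = 1.25 |
|---|---|---|---|
| Control-arm median (true 0) | about 0 | about +12 points | about −10 points |
| Type I error | 0.046–0.048 | 0.050 | 0.050 |
| Power | 0.87–0.88 | 0.85 | 0.85 |
| Between-arm median difference | 19.7–19.8 points | 21.9 points | 17.6 points |

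A closed-form check agrees. With equal halves, the median sits midway on the log scale, so the control median is 1/√0.8 − 1 = +11.8% or 1/√1.25 − 1 = −10.6%.

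**The case against.** The strongest reply is that Protocol 7.8.1 already ties the fasting rule to the assay and not to the date of joining. A stored sample not drawn fasting would then not be a valid marker sample, and the late-joiner clause would serve romosozumab level, sclerostin, iPTH and novel biomarkers. On that view only a clarification is missing. This has weight but does not settle the matter. The clause speaks of sub-study analyses without exception, a late joiner has no other Day 1 sample, and the SAP applies no screen that would enforce the rule.

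Three stronger readings are tempting, and the documents support none of them:
- **That the stored samples were non-fasting.** The visit list is silent on fasting. It shows that fasting was not required, not that the women had eaten or were drawn after noon.
- **That every percent change in the sub-study is distorted.** Women enrolled before Day 1 are unaffected, as are late joiners' changes between two draws made under the same conditions.
- **That the arm comparison is biased.** Baseline precedes treatment, and nothing in the documents links late joining to arm, so the test keeps its level.

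It is also fair to say that the route may never be used, that the direction and size of f are unknown, and that no recording of fasting status is described. Protocol 7.8.1 has collection date and time entered in the medical record, which can verify only the before-noon part. All of this stands and limits the point to a conditional one.

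**Conclusion.** The gap holds in a limited form. If the route is used, the plan lets turnover-marker baselines come from draws to which no fasting or before-noon rule applied. That is contrary to Protocol 7.8.1 and 7.8.2, and SAP 7.8.2 does not screen for it.

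At most about 100 of about 200 women are concerned, and for them only the percent changes at visits after joining. The shift can go either way. At the outer values of the assumed range for f, and with half the sub-study joining late, an arm median could move by roughly 10 to 12 points. The between-arm rank test remains valid provided late joining is balanced across arms. In the simulation its power fell by 2 to 3 percentage points, and the estimated difference changed by about 2 points. These endpoints lie outside the testing sequence in SAP 10.1, so no confirmatory conclusion is touched. The change is still worth making, because the within-arm marker profile is reported in its own right.

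**What to change.** In SAP 7.8.2 and 10.7.1:
- Flag every woman whose sub-study consent is dated after Day 1.
- Report percent changes in P1NP, sCTX, BSAP and OC with women excluded who lack a Day 1 sample documented as fasting and drawn before noon under Protocol 7.8.2. At minimum, make this a pre-specified sensitivity analysis beside the all-subject result.
- To make the exclusion workable, treat a flagged woman as not meeting the rule unless fasting and collection time are documented. Treat a woman who consented by Day 1 as meeting it unless a deviation is recorded, since her visit list required it.
- Keep stored samples for romosozumab level, sclerostin and iPTH, which the visit lists do not require to be fasting.

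The cost is a few SAP sentences and one derived flag, plus site queries if the sponsor wants to recover fasting status for flagged women. The downside is fewer women in the restricted analysis, up to half the sub-study in the extreme case. Showing the all-subject result beside it limits that loss.
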